Explanation: The purpose of H1 is to examine the effectiveness of EMR. If H1 is supported, this could establish EMR as the gold-standard practice for post-acute rehabilitation. Our primary analysis is the change from baseline to Discharge. This single primary endpoint allows for an effectiveness test that is not confounded by length of stay differences or post-discharge issues beyond the reach of EMR.

2. Aim 2: Examine EMR's ability to overcome patient-level barriers to successful rehabilitation.

H2: The effectiveness of EMR for functional recovery will be greatest in: (a) patients with clinical depression; (b) patients with high levels of medical comorbidity; (c) patients with cognitive impairment.

Explanation: EMR was designed to overcome barriers to rehabilitation (for example, due to depression); therefore, the difference in functional recovery between EMR and SOC should be greater in the most vulnerable older adults. If H2 is supported, we will demonstrate that older adults with these common comorbidities benefit the most from high intensity, high engagement rehabilitation. If so, this would refute conventional wisdom in post-acute rehabilitation, codified in admission criteria for rehabilitation facilities, regarding the appropriate candidates for rehabilitation (as described in Significance).

3. Aim 3 (Secondary): Effect of EMR on MADRS scores on individuals with clinical depression.
4. Calculated a rate of clinical depression (SCID for those with elevated MADRS score):

22 participants had the SCID administered.

8 did not have depression diagnosis while 14 did have depression diagnosis.

Conclusion: only 14 individuals in the study had a clinical depression (ie, a diagnosis of depression). No further analyses to be done.

Additional Variables/Outcomes

6-Minute Walk/Gait Speed: Administered at Baseline and Discharge. Two components for 6-Minute Walk:

- 1) Distance Ambulated (feet): text box. If unable to complete, distance was entered as a 0.
- 2) Time: options are 6 minutes, Other time (MM:SS), and N/A

Two components for Gait Speed (Baseline, Day 30, Discharge):

- 1) Distance: radio button (10 meters, 4 meters, 0 meters). If unable, 0 meters selected.
- 2) Time (seconds): text box (if unable, time is 0).

Disposition (i.e., discharge to community vs. not)

Rehospitalization (rate).

Secondary analyses (not for main paper):

1. PANAS (A positive and a negative affect score).

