- b. Medical illness preventing study participation or accurate data collection (e.g., highly unstable cardiac illness such that early re-hospitalization is expected; metastatic or other cancer such that hospice is recommended or survival is limited).
- c. Moderate-severe dementia (demonstrated by chart diagnosis and/or short blessed score greater than 13).
- d. Progressive neurological condition such that recovery of function is not feasible.
- e. Patient did not have the ability to walk prior to hospitalization (e.g. paraplegic).
- f. Schizophrenia or other chronic or current psychotic disorder.
- g. Patient normally resides in a long-term care facility.

- iii. Recruitment: the numbers that will be presented in a CONSORT diagram include:
 - 1. # Screened/Consented and reasons for ineligibility.
 - 2. # Randomized to EMR vs SOC.
 - 3. # Present at each follow-up time point (i.e., Day 30, Discharge, Day 60, and Day 90); reasons for discontinuation/lost to follow-up.
 - 4. # Included in Final Analysis; reasons excluded from final analysis.
- iv. Withdrawal/follow-up

No follow-up was done for withdrawn participants. If a participant was withdrawn, then an attempt was made to obtain final prognosis information using clinical data available from the chart unless explicitly told not to do so by the participant.

v. Baseline Patient Characteristics

In addition to the screening variables described above, the variables below will also be summarized in a Baseline Characteristics Table. Continuous variables will be summarized using median and IQR while categorical variables will be summarized using counts and percentages. These statistics will be provided by condition (EMR Vs SOC) and as a whole.

- Barthel Index
- MADRS Score
- Gait Speed (Distance in meters and Time in seconds)
- 6-Minute Walk (Distance Ambulated, in feet)
- PANAS Score
- Short Blessed Test Score
- CIRS-G Score
- Clock Drawing Score

Analysis:

i. Outcome Definitions

- 1) Aim 1: Examine the effectiveness of EMR for improving functional outcomes in older adults admitted to SNFs for post-acute rehabilitation.

H1: EMR will improve functional recovery to a greater extent than standard-of-care rehabilitation.

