The primary measure employed for assessing functional improvement will be The Barthel Index. This index is a 10-item scale used to ascertain the degree of independence of normal daily activities. This will be done by taking the sum of these 10 items. A high score indicates a high degree of independence, and a score can range from 0 to 100.

- 2) Aim 2: Examine EMR's ability to overcome patient-level barriers to successful rehabilitation.

H2: The effectiveness of EMR for functional recovery will be greatest in: (a) patients with clinical depression; (b) patients with high levels of medical comorbidity; (c) patients with cognitive impairment.

Part (a) will be assessed using the MADRS, which is a 10-item scale used to assess for major depression. Each item is rated on a scale of 0 to 6, where a 6 is worse. The total score (i.e., sum of these 10 items) will be

used to assess for major depression and can range from 0 to 60.

Part (b) will be assessed using the CIRS-G, which is a 13-item scale used to assess for disease in all major body systems. Each item is rated on a scale of 0 to 4, with a 4 indicating severe impairment. The total score (i.e., sum of these 10 items) will be used to assess for medical comorbidity and can range from 0 to 52.

Part (c) will be assessed using the SBT Scores. The SBT is a 6-item scale used to assess for memory/concentration deficits. A total score, which is obtained after applying a weighting factor to each item then summing up the final item scores, can range from 0 to 28. A high score indicates impairment consistent with dementia.

ii. Analysis Methods

The primary outcome analysis for functional recovery will use a marginal model with time (baseline and discharge), condition (E-MR vs. SOC) and time x condition as fixed effects and with a covariance structure specified based on the Bayesian Information Criterion (BIC). Employing a marginal model allows for a more robust approach in the handling of missing data compared to the traditional ANCOVA model.

For H2 under Aim 2, each potential continuous moderator will be individually inserted into the primary model. The term of interest will be the time x condition x moderator interaction.

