The secondary analyses for Six-Minute Walk distance and Gait Speed will use a Mann-Whitney U Test to test for differences in means between groups. In addition, a Chi-Square test will be employed to test for independence between condition and the secondary outcome variable re-hospitalization. Finally, the outcome of self-reported function will use a marginal model using time (30, 60, and 90 days), condition and time x condition as fixed effects, with a covariance structure specified based on BIC.

Exploratory analyses will also test whether the effects of age, gender, race and site (i.e., Barnes Jewish Extended Care Vs Alexian Brothers Sherbrooke Village) altered the conclusions of the primary results as well as the conclusions of the moderator results.

Note: we will not look at the nesting of subjects within therapists who are then nested within site as this is not possible due to the inconsistency of assigning therapists to participants.

iii. Missing Data

We use a marginal model which accounts for missing data (no multiple imputation was used).

iv. Harms

An adverse event (AE) is any untoward medical occurrence in a subject temporally associated with participation in the clinical study or with use of the experimental agent being studied. An adverse finding can include a sign, symptom, abnormal assessment (laboratory test value, vital signs, electrocardiogram finding, etc.), or any combination of these.

AEs will be labeled according to severity (i.e., mild, moderate or severe), which is based on the AE's impact on the participant.

AEs will be categorized according to the likelihood that they are related to the study intervention or other study procedures (i.e., definitely unrelated, definitely related, probably related, or possibly related).

SAEs that are unanticipated, serious, and possibly related to the study intervention will be reported to the IRB, and NIMH in accordance with requirements. Unexpected fatal or life-threatening AEs related to the intervention will be reported to the NIMH Program Officer within 7 days. Other serious and unexpected AEs related to the intervention will be reported to the NIMH Program Official within 15 days. Anticipated SAEs will be handled in a less urgent manner but will be reported to the IRB in accordance with their requirements.

v. Statistical Software

All analyses will be performed using SAS and/or R.

vi. References

none

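### The SAP's only missing-data rule covers the marginal-model outcomes; six-minute walk, gait speed and rehospitalisation are left to observed-case tests that ignore the baseline walk measures

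*SAP*

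**What the plan says.** The SAP's section on missing data (Analysis iii) is one sentence: "We use a marginal model which accounts for missing data", with a note that multiple imputation was not used. It names no outcome, analysis set or sensitivity analysis.

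Analysis ii specifies marginal models in two places. One is the Barthel Index at baseline and discharge, where the stated reason is that "Employing a marginal model allows for a more robust approach in the handling of missing data compared to the traditional ANCOVA model". The other is self-reported function at Days 30, 60 and 90. For the performance measures, "The secondary analyses for Six-Minute Walk distance and Gait Speed will use a Mann-Whitney U Test to test for differences in means between groups". Rehospitalisation gets a chi-square test. The SAP does not say whether the walk tests use the follow-up value or the change, which occasion is tested for gait speed, or what window and denominator apply to rehospitalisation.

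Two other provisions matter. Under Additional Variables/Outcomes, a participant unable to do the six-minute walk is entered as 0 feet, and one unable to do the gait test as 0 meters and 0 seconds. Under Withdrawal/follow-up, "No follow-up was done for withdrawn participants", but final prognosis information was sought from the chart unless the participant refused. The protocol (section G3) promises only a technique suited to the analysis.

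**The concern.** Neither a Mann-Whitney test nor a chi-square can use a participant who has no value. With imputation ruled out and no other rule given, these outcomes default to observed cases, although the SAP reads as if missing data were dealt with. The SAP prefers the marginal model to ANCOVA because of missing data, yet gives the walk outcomes a test that lacks even ANCOVA's baseline adjustment. Both walk measures are taken at baseline, so the information is there.

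Some loss is plausible. Withdrawn participants had no further visits, the discharge walk is done at the SNF (protocol F6), patients know their allocation, and one arm receives more intense therapy. If weaker walkers leave more often in one arm, the walk tests compare differently selected groups. Even without that, ignoring baseline costs precision.

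**Working it through.** The plan gives no rate of loss, overall or by arm, and no baseline-to-follow-up correlation. There is therefore no plan figure to reproduce, and size can only be shown under assumptions.

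**Step 1. What the sentence covers.**

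| Outcome | SAP analysis | Participant with a baseline but no follow-up value |
|---|---|---|
| Barthel | Marginal model, baseline and discharge | Stays in |
| Self-reported function | Marginal model, Days 30/60/90 | Contributes any of the three visits attended |
| Six-minute walk, gait speed | Mann-Whitney | Drops out |
| Rehospitalisation | Chi-square | Dropped, counted as no event, or chart-derived: not stated |

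**Step 2. When loss biases the walk tests.** From the documents: 252/2 = 126 per arm and a 5% level. Assumed: standard normal baseline and follow-up, correlation 0.6, no EMR effect. Let loss at overall rate p fall only on the half below average at baseline, whose mean is −0.798 SD. The mean baseline of those retained is then 0.798 × p/(1 − p), and the bias in the follow-up difference (EMR minus SOC) is

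0.6 × 0.798 × [p_E/(1 − p_E) − p_S/(1 − p_S)].

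- 10% in both arms: 0.
- 10% EMR, 20% SOC: 0.479 × (0.111 − 0.250) = −0.067 SD.
- 10% EMR, 30% SOC: 0.479 × (0.111 − 0.429) = −0.152 SD.

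Simulation (2,000 trials each) gives −0.069 and −0.154 SD. Mann-Whitney error is 8.8% and 18.8%, against 5.0% in both cases with baseline adjustment. With the same unequal rates but loss unrelated to walking, Mann-Whitney error is 4.7% and 5.1%. Unequal rates alone do no harm.

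**Step 3. Graded loss.** The rule in step 2 is harsh: 30% overall means losing 60% of the weaker half and none of the stronger. With loss rising smoothly as baseline walking falls (logistic slope per SD), results on follow-up values are:

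| Assumed loss | Mann-Whitney error |
|---|---|
| 20% in both arms, random or same slope | about 5–6% |
| 20% in both arms, tied to baseline in SOC only, slope 1.0 / 1.5 | about 11% / 15% |
| Slope 1.0 in both arms, 30% SOC and 10% EMR | about 11% |
| Slope 1.0 in both arms, 20% SOC and 10% EMR | about 6% |
| 10% in both arms, SOC only, slope 1.0 / 1.5 | 6.6% / 8.3% |
| 5% in both arms, SOC only, either slope | 5.4% |

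The baseline-adjusted model stays at about 5–6% throughout; adjusted ranks also hold with 15% of values at zero. If change scores are tested instead, the two SOC-only cases at 20% loss give about 8–11% with bias of the opposite sign. The direction of any distortion therefore depends on a choice the SAP does not state.

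**Step 4. Limit of the remedy.** If loss is concentrated in participants with low follow-up values (10% against 20–30%), Mann-Whitney error is 14.5–48.1% and the baseline-adjusted model also fails, at 9.8–32.6%.

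**Step 5. Precision with random loss.** Assume 10% loss and d = 0.4: n = 126 × 0.9 = 113.4 per arm, and the standard error is √(2/113.4) = 0.1328.

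- Mann-Whitney: 0.4/0.1328 × √(3/π) = 3.012 × 0.977 = 2.943. Power = Φ(2.943 − 1.960) = Φ(0.98), about 84%.
- Rank ANCOVA: correlation 0.6 gives a rank correlation of (6/π) × arcsin(0.3) = 0.582. Residual factor √(1 − 0.582²) = 0.813. Power = Φ(2.943/0.813 − 1.960) = Φ(1.66), about 95%.

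Simulation gives the same two figures.

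**Step 6. Rehospitalisation.** Assume a true rate of 20% in both arms, with rehospitalised patients twice as likely to be missing. With missing fraction m, q = m/(2 × 0.2 + 0.8) and the observed rate is 0.2 × (1 − 2q)/(1 − m).

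- m = 10%: q = 0.083, observed 18.5%.
- m = 20%: q = 0.167, observed 16.7%.
- m = 30%: q = 0.25, observed 14.3%.

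Loss of 10% in EMR against 20–30% in SOC would thus create an apparent gap of about 2–4 points, unless chart data fill it.

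**The case against.** Much of the case on the other side stands. The SAP keeps the most obviously informative group in the data: those unable to walk are scored 0, and for six-minute walk they take the lowest rank. Chart retrieval may recover some rehospitalisations. The CONSORT commitments (numbers present at each time point, with reasons for loss and exclusion) would expose differential loss. The protocol expects missing data mainly after discharge, whereas the discharge walk is done at the facility near that date. Observed-case analysis is an inference from the tests chosen, not SAP wording, and the missing-data sentence can be read as describing the primary model alone. A rank test is also a reasonable choice for skewed data with zeros.

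A reader might infer that unequal dropout by itself biases these tests, that the weakest walkers vanish from them, or that the trial's walk results are biased. The documents support none of these. Unequal loss alone leaves the error near 5%, inability is recorded, and no loss rate or pattern is reported. Nor does a marginal model make the problem go away, since it relies on data being missing at random.

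Three things remain. Even on the narrow reading, these outcomes have no rule. The 0-over-0 gait entry has no stated conversion to a speed, so non-walkers could still fall out of that test. And a rank test can be adjusted for baseline, so skewness is no reason to discard baseline.

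**Conclusion.** The point holds in limited form. The missing-data statement does not reach six-minute walk, gait speed or rehospitalisation, and the walk tests leave collected baseline data unused. The exposure is conditional: about 6–15% error instead of about 5–6% if loss is graded by baseline walking and differs by arm at about 20% average loss, close to nominal at 5% loss, and none if the loss mechanism is the same in both arms. The less conditional cost is power, about 84% against 95% for an assumed d of 0.4, correlation of 0.6 and 10% random loss. The correlation, loss rates and loss mechanisms are all assumptions. The outcomes are secondary and the primary Barthel analysis is unaffected.

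**What to change.** - Analyse six-minute walk and gait speed at discharge in a marginal or ANCOVA model conditioning on the baseline value, on ranks given the skew and zeros. State that gait speed is 0 when distance and time are both 0. Keep Mann-Whitney as a sensitivity test, and say whether it uses follow-up or change values.
- Limit the Missing Data sentence to outcomes modelled this way, state that they rely on missing at random, and add a sensitivity analysis that varies the assumption by arm.
- Using the Day 30 gait speed as a further occasion is optional. Stays average about 3 weeks, so discharge can fall on either side of Day 30 and the two are not simply ordered.
- For rehospitalisation, state the window, the denominator and whether chart-derived status counts. A time-to-event analysis is optional, since censoring at last contact also assumes uninformative loss.

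The cost is a dated SAP addendum and two re-specified models on data already collected. The price is a rank or distributional assumption, and an adjusted rank effect is harder to express in feet or meters per second, so descriptive summaries in those units should accompany it.
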